## PROTOCOL AMENDMENT SUMMARY OF CHANGES TABLE

DOCUMENT HISTORY	
Document	Date
Amendment 02	25-Oct-2017
Amendment 01	24-May-2017
Original Protocol	13-Mar-2017

**Amendment 02:** 25-Oct-2017

**Overall Rationale for the Amendment:** Relocation of Sponsor, etc. (See below table)

Section # and Name	Description of Change	Brief Rationale
TITLE PAGE	
Changed from:
 
Sponsor Name and Legal Registered Address:
 
GlaxoSmithKline K.K. (GSK)
 
[name]
 
Changed to:
 
Sponsor Name and Legal Registered Address:
 
GlaxoSmithKline K.K. (GSK)
 
[name]
	Relocation of Sponsor
2. SCHEDULE OF ACTIVITIES (SOA)	
Changed from:
 
Table 1. SCHEDULE OF ACTIVITIES
 
Procedure; Serum pregnancy test
 
Visit 1, 4, 5, 7, Early Withdrawal; X
 
Footnote 6.
 
Assessments at only Visit1 to be conducted in all females. Assessments at Visit except for the Visit 1 only to be conducted in females of
	To align with on-going 205715 study

Section # and Name	Description of Change	Brief Rationale
	
reproductive potential.
 
Changed to:
 
Table 1. SCHEDULE OF ACTIVITIES
 
Procedure; Serum pregnancy test
 
Visit 1, 4, 5, 7, Early Withdrawal; X
 
Footnote 6.
 
Assessments are only to be conducted in females of reproductive potential.
	
12.2. Appendix 2: Study Governance Considerations	
Study Period
 
Changed from: June 2017 ~ Mar 2019
 
Changed to: June 2017 ~ Sep 2019
	Extension of recruitment periods
12.2. Appendix 2: Study Governance Considerations	
Sponsor Information Page
 
Changed from:
 
Sponsor Legal Registered Address:
 
GlaxoSmithKline K.K. (GSK)
 
[name]
 
Study Director: PPD [REDACTED], Head of Respiratory TA Office, Medicines Development
 
Sponsor Contact Address:
 
Leading Author : PPD [REDACTED], Respiratory TA Office, Medicines Development
 
TEL : PPD [REDACTED]
 
FAX : PPD [REDACTED]
 
Sponsor's Contact Information (10:00-18:00, Monday to Friday, except national holidays,
	Relocation of Sponsor

Section # and Name	Description of Change	Brief Rationale

## 1. SYNOPSIS

**Protocol Title:**

A Phase III, 52-week, Open-label Study to Evaluate Long-term Safety of Fixed Dose Combination Therapy Fluticasone Furoate/Umeclidinium Bromide/Vilanterol Trifénatate in Japanese Patients with Asthma

**Short Title:**

A Long-term Safety Study of Fixed Dose Combination Therapy Fluticasone Furoate/Umeclidinium Bromide/Vilanterol Trifénatate in Japanese Patients with Asthma

**Rationale:**

Despite availability of treatments and published guidelines, patients may have asthma that is inadequately controlled. The prevalence of inadequately controlled asthma varies based on the definition used for control. In a sample of asthmatics visiting their healthcare provider for any reason, 58% of adult asthmatics were estimated to have uncontrolled asthma based on the Asthma Control Test (ACT, defined as an ACT score  $\leq 19$ ).

The Global Initiative for Asthma (GINA) guidelines recommend include a long-acting muscarinic antagonist (LAMA) as add-on treatment option for adults with asthma that are currently taking medium to high dose inhaled corticosteroid/long-acting  $\beta_2$  agonist (ICS/LABA) treatment and have a history of exacerbations. Exacerbations are an important endpoint in asthma therapy; however, symptom control is also important in determining what patients could benefit from step-up therapy. Data from the GlaxoSmithKline (GSK) Phase IIb study 200699 demonstrated that the LAMA/umeclidinium (UME), when added to the ICS fluticasone furoate (FF), reduced salbutamol use and improved symptoms in a sub-group of subjects with the primary diagnosis of asthma.

[figure not shown]
GSK is currently developing a once-daily 'closed' triple therapy of an ICS/LAMA/LABA combination [FF/UME/VI] in a single device, with the aim of providing a new treatment option for the management of asthma by improving lung function, health-related quality of life (HRQoL) and symptom control over established combination therapies. The objective of this study is to evaluate long-term safety of fixed dose combination therapy FF/UME/VI in Japanese patients with asthma. A global study comparing FF/UME/VI with a standard of care ICS/LABA combination therapy (Study 205715) is ongoing in parallel with this study, which will provide important information to prescribers regarding the benefit of step-up to closed triple therapy to patients uncontrolled on ICS/LABA.

**Objectives and Endpoints:**

Objective	Endpoint
Primary	

 
To evaluate the safety of long-term treatment with FF/UMEV/VI combination therapy
 
	
 
Incidence and type of adverse events (AE)/serious adverse events (SAE)
 

Secondary	

 
To evaluate the safety of FF/UMEV/VI combination therapy
 
	
Secondary Endpoints
 
 
Blood pressure/pulse measurements
 
12-lead Electrocardiogram (ECG)
 
Clinical laboratory tests (hematology , biochemistry and urinalysis)
 

Other	

 
To evaluate the efficacy of FF/UMEV/VI combination therapy
 
	
Other Endpoints
 
 
Mean change from baseline in trough Forced Expiratory Volume in 1 second (FEV1) at Week 24 and Week 52
 
Mean change from baseline in Asthma Control Questionnaire – 7 (ACQ-7) total score at Week 24 and Week 52
 
Mean change from baseline in St. George's Respiratory Questionnaire (SGRQ) total score at Week 24 and Week 52
 
Mean change from baseline in the Asthma Quality of Life Questionnaire (AQLQ) total score at Week 24 and Week 52
 
Unscheduled asthma-related healthcare resource utilization over the 52 weeks of the treatment period
 
Annualized rate of severe asthma exacerbations
 
Annualized rate of moderate/severe asthma exacerbations
 

## Overall Design:

The present study is a phase III, multicenter, non-comparator, non-randomized, open-label study in Japanese patients with asthma to evaluate long-term safety of FF/UMEV/VI 100/62.5/25 micrograms (mcg) and FF/UMEV/VI 200/62.5/25 mcg.

\* Switching medication from FF/UMEV/VI 100/62.5/25 mcg to FF/UMEV/VI 200/62.5/25 mcg will be permitted in accordance with the control status of the subject assessed by ACQ-7 at Week 24 of the treatment period.

Eligible patients who meet the pre-defined criteria at screening (Visit 1) will enter into a 2-week run-in period. During the run-in period, the subjects will continue their pre-screening inhaled medications for asthma (ICS+LABA or ICS+ LABA+LAMA) until the day before Visit 2 without any change in regimen/dosage. After completion of the run-in period, subjects who meet pre-defined criteria at Visit 2 will be allocated to either FF/UMEV/VI 100/62.5/25 or FF/UMEV/VI 200/62.5/25 treatment depending on the asthma control status with inhaled asthma therapy during the run-in period as shown in the table below, and initiate a 52-week treatment period. Only at Week 24 of the treatment period (Visit 5), switching medication from FF/UMEV/VI 100/62.5/25 to FF/UMEV/VI 200/62.5/25 will be permitted if the control status of the subject assessed by ACQ-7 is not well controlled (i.e., ACQ score >0.75).

**Correspondence between Asthma Control Status with inhaled Asthma Therapy during the run-in period and Allocated Study Treatment**

Group	Asthma control status with inhaled asthma therapy 	Allocated study treatment
Group 1	Not well controlled with ICS (mid-dose)+LABA or Controlled with ICS (mid-dose)+LABA + LAMA	FF/UMEC/VI 100/62.5/25 mcg via ELLIPTA, once-daily, 1 puff/time, morning
Group 2	Not well controlled with ICS (high-dose)+LABA or Not well controlled with ICS (mid-dose)+LABA + LAMA or Controlled with ICS (high-dose)+LABA + LAMA	FF/UMEC/VI 200/62.5/25 mcg via ELLIPTA, once-daily, 1 puff/time, morning

1. Asthma Control Questionnaire (ACQ-6 at screening and ACQ-7 at Week 0, week 24, week52/Withdrawal) will be used for the assessment of control status of asthma, i.e., $\leq$ 0.75 points shows controlled and  $>0.75$  shows not well controlled.

**Number of Participants:**

The number of asthmatic adult subjects (with the control status on inhaled asthma therapy with medium to high dose ICS + LABA or medium to high dose ICS + LAMA + LABA [as shown in the table above]) required to be enrolled in this study is 110 (a total number of subjects to be allocated in Group 1 [FF/UMEC/VI 100/62.5/25] and Group 2 [FF/UMEC/VI 200/62.5/25]). According to the ICH guidelines, the sample size of 110 subjects would allow 100 subjects to complete the 52-week treatment period, assuming a drop-out rate of approximately 10%.

**Treatment Groups and Duration:**

This is a 55-week study consisting of the following three study periods:

- Run-in period (2 weeks): Eligible patients who meet the pre-defined criteria at screening (Visit 1) will enter into a 2-week run-in period. During the run-in period, the subjects will continue their pre-screening inhaled medications for asthma (ICS+LABA or ICS+LABA+LAMA) until the day before Visit 2 without any change in regimen/dosage.
- Treatment period (52 weeks): subjects who meet pre-defined criteria at Visit 2 will be allocated to either FF/UMEC/VI 100/62.5/25 or FF/UMEC/VI 200/62.5/25 treatment depending on the asthma control status with inhaled asthma therapy during the run-in period, and initiate a 52-week treatment period.

Switching medication from FF/UMEC/VI 100/62.5/25 to FF/UMEC/VI 200/62.5/25 will be permitted in accordance with the control status of the subject assessed by ACQ-7 at Week 24 of the treatment period (Visit 5).

- Follow-up period (1 week): A safety follow-up telephone contact or clinic visit will be conducted at the end of the follow-up period.

## 2. SCHEDULE OF ACTIVITIES (SOA)

Table 1 SCHEDULE OF ACTIVITIES

Procedure	Pre-screen	Run-in	Treatment period							Follow-up
Visit	0	1 Screening	2 Baseline	3	4	5	6	7 End of Treatment (EOT)	Early Withdrawal (EW)	Safety follow-up contact
Day	-28 to -14	-14	1	29	85	169	253	365		
Week	-4 to -2	-2	0	4	12	24	36	52		
Window		-3		-5/+2d	-5/+2d	-5/+2d	-5/+2d	-5/+2d		
Informed consent 	X									
Genetics/Pharmacogenetic informed consent 	X									
Inclusion and exclusion criteria		X	X							
Demography	X									
Past and current medical conditions including asthma history  and exacerbation history		X								
Smoking history and status		X								
Concomitant medication review		X	X	X	X	X	X	X	X	X
Allocation/registration 			X							
Register visit in IRT (RAMOS NG) 	X	X	X	X	X	X	X	X	X	X
Safety Assessment										
Physical examination		X				X		X	X	
Weight/height		X								
Adverse events			X	X	X	X	X	X	X	X
Serious adverse events	X	X	X	X	X	X	X	X	X	X
Vital signs (blood pressure and pulse rate)		X	X	X	X	X	X	X	X	
ECG		X		X		X		X	X	
Hematology and clinical chemistry		X			X	X		X	X	
Urinalysis		X			X	X		X	X	
Serum pregnancy test 		X			X	X		X	X	
Urine pregnancy test 			X	X			X			

Procedure	Pre-screen	Run-in	Treatment period							Follow-up
			2 Baseline	3	4	5	6	7 End of Treatment (EOT)	Early Withdrawal (EW)	
Visit	0	1 Screening								Safety follow-up contact
Day	-28 to -14	-14	1	29	85	169	253	365		
Week	-4 to -2	-2	0	4	12	24	36	52		
Window		-3		-5/+2d	-5/+2d	-5/+2d	-5/+2d	-5/+2d		
Other Assessment										
ACQ 		X 	X 			X 		X 	X 	
SGRQ 			X			X		X	X	
AQLQ 			X			X		X	X	
Pre-dose spirometry 			X			X		X	X	
Moderate/severe asthma exacerbation			X	X	X	X	X	X	X	X
Genetics/Pharmacogenetic sampling 			X							
Dispense paper Medical Problems/Medications Taken worksheet	X	X	X	X	X	X	X	X	X	
Review paper Medical Problems/Medications Taken worksheet		X	X	X	X	X	X	X	X	X
Healthcare resource utilization			X	X	X	X	X	X	X	
Dispense investigational product			X	X	X	X	X			
Collect investigational product				X	X	X	X	X		X
Dispense salbutamol (as required)		X	X	X	X	X	X			
Collect salbutamol (as required)			X	X	X	X	X	X	X	

1. The Informed Consent Form (ICF) must be signed before any study procedures, including medication cessation.
2. Genetics/Pharmacogenetic research consent may be obtained at the same time as the study Informed Consent and must be obtained prior to obtaining a Genetics/pharmacogenetic blood sample.
3. The assessment of asthma history will include: the age of the subject when they were first provided with an inhaler for asthma; completion of an asthma medical history questionnaire (a copy of this questionnaire and instructions for its use can be found in the SRM).
4. Subjects must not be allocated prior to confirming their eligibility to participate in the study.
5. The IRT will be used for allocation, and study treatment supply management (Please refer to the RAMOS NG IRT manual and SRM for more information).
6. Assessments are only to be conducted in females of reproductive potential.
7. Assessment(s) to be completed before any study procedures .Study treatment should be administered at the same time of day each applicable clinic visit,
8. Assessment to be conducted by using ACQ-6
9. Assessment to be conducted by using ACQ-7

10. Spirometry to be performed after withholding rescue medication for at least 6 hours and prior to taking the morning dose of study treatment. Pre-dose spirometry assessments should be performed at the same time of day at each applicable visit.
11. Pharmacogenetic sample may be drawn any time from Visit 2 onwards.

ACQ: Asthma Control Questionnaire, AQLQ: Asthma Quality of Life Questionnaire, IRT: Interactive Response Technology, SGRQ: St. George's Respiratory Questionnaire

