**Figure 1 Study Schematic**

Eligible patients who meet the pre-defined criteria at screening (Visit 1) will enter into a 2-week run-in period. During the run-in period, the subjects will continue their pre-screening inhaled medications for asthma (ICS+ LABA or ICS+LABA+ LAMA) until the day before Visit 2 without any change in regimen/dosage. After completion of the run-in period, subjects who meet pre-defined criteria at Visit 2 will be allocated to either FF/UMEV/VI 100/62.5/25 mcg (Group 1) or FF/UMEV/VI 200/62.5/25 mcg (Group 2) depending on the asthma control status with inhaled asthma therapy during the run-in period (see [Table 2](#)), and initiate a 52-week treatment period. Only at Week 24 of the treatment period (Visit 5), switching medication from FF/UMEV/VI 100/62.5/25 mcg to FF/UMEV/VI 200/62.5/25 mcg will be permitted if the control status of the subject assessed by ACQ-7 is inadequate (i.e., ACQ score >0.75). As a rescue medication, salbutamol is permitted throughout the run-in and treatment periods.

**Table 2 Correspondence between Asthma Control Status with Inhaled Asthma Therapy during the run-in period and Allocated Study Treatment**

Group	Asthma control status with inhaled asthma therapy 	Allocated study treatment
Group 1	Not well controlled with ICS (mid-dose)+LABA or Controlled with ICS (mid-dose)+LABA + LAMA	FF/UMEV/VI 100/62.5/25 mcg via ELLIPTA, once-daily, 1 puff/time, morning
Group 2	Not well controlled with ICS (high-dose)+LABA or Not well controlled with ICS (mid-dose)+LABA + LAMA or Controlled with ICS (high-dose)+LABA + LAMA	FF/UMEV/VI 200/62.5/25 mcg via ELLIPTA, once-daily, 1 puff/time, morning

1. Asthma Control Questionnaire (ACQ-6 at screening and ACQ-7 at week 0, week 24, week52/Withdrawal) will be used for the assessment of control status of asthma, i.e.,  $\leq 0.75$  points shows controlled and  $>0.75$  shows not well controlled.

Subjects will visit the clinic/hospital at screening (Visit 1), Week 0 (Visit 2), Week 4 (Visit 3), Week 12 (Visit 4), Week 24 (Visit 5), Week 36 (Visit 6), Week 52 (Visit 7/End of Treatment [EOT]) or Early Withdrawal (EW) , and about one week after Week 52 (Visit 7/EOT) or EW Visit as a safety follow-up visit.. Telephone contact can be selected for follow-up period.

This study consists of three periods as described below: run-in, treatment and follow-up periods. Details of study procedures and assessments in these periods are provided in the Study Reference Manual (SRM).

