**Table 4 Description of Study Treatment**

Investigational product:	FF/UME/VI	
Dosage formulation:	ELLIPTA with 30 doses of inhalation powder (2 strips with 30 blisters per strip)	
Unit dose strengths/ dosage levels:	Strip 1: FF blended with lactose 100 or 200 mcg per blister	Strip 2: UME/VI blended with lactose and magnesium stearate UME/VI 62.5 mcg and VI 25 mcg per blister
Route of administration	Inhaled	
Dosing instructions:	1 puff at approximately the same time in each morning	
Packaging and labelling	Each will be labeled as required per country requirement.	
Manufacturer	GSK	

Subjects will self-administer their first dose in the clinic and will continue to administer FF/UME/VI at approximately the same time each morning for the duration of the treatment period. Each subject will be instructed on the proper use of the ELLIPTA and will inhale once from the ELLIPTA each morning.

At Visit 1, an salbutamol metered-dose inhaler (MDI) as rescue medication will be provided for as-needed use throughout the study period starting at Visit 1. At the Investigator's discretion, more than one MDI may be provided at any one time. Salbutamol will be sourced from local commercial stock. The contents of the label will be in accordance with all applicable regulatory requirements in Japan.

All used and unused study treatment and salbutamol will be returned to GSK at the end of the study to be available for disposal. Detailed instructions for the return of the study drug can be found in the SRM.

If any ELLIPTA fails to function properly, the subject should return to the clinic as soon as possible to obtain a new inhaler.

In addition, any ELLIPTA that fails to function properly must be identified and returned to GSK for testing.

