**Table 5      Study Treatment Assignment**

Group	Current inhaled therapy and control status of asthma during the run-in period 	Study treatment
Group 1	Not well controlled with ICS (mid-dose)+LABA or Controlled with ICS (mid-dose)+LABA + LAMA	FF/UMEC/VI 100/62.5/25 mcg via ELLIPTA, once-daily, 1 puff/time, morning
Group 2	Not well controlled with ICS (high-dose)+LABA or Not well controlled with ICS (mid-dose)+LABA + LAMA or Controlled with ICS (high-dose)+LABA + LAMA	FF/UMEC/VI 200/62.5/25 mcg via ELLIPTA, once-daily, 1 puff/time, morning

1. ACQ-7 score (Week 0) will be used for the assessment of control status of asthma, i.e.,  $\leq 0.75$  points shows controlled and  $>0.75$  shows not well controlled.

On the morning of scheduled clinic study visit at Visit 2, Visit 5 and Visit 7, subjects will refrain from taking their morning dose of study treatment until instructed to do so by clinic personnel.

Study treatment will be taken at the clinic at approximately the same time of day as taken at Visit 2. Each Investigator will be provided with sufficient supplies to conduct the trial. Additional treatment packs will be supplied as needed to the sites.

The last dose of the investigational product will be taken at the clinical at Visit 7/EOT (or at the early withdrawal visit as appropriate) and safety follow-up assessments will be performed approximately 1 weeks later.

At Week 24 of the treatment period (Visit 5), switching medication from FF/UMEC/VI 100/62.5/25 mcg to FF/UMEC/VI 200/62.5/25 mcg will be permitted if the control status of the subject assessed by ACQ-7 is inadequate (i.e., ACQ score  $>0.75$ ).

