## 7.6. Treatment Compliance

When subjects are dosed at the study site, they will receive study treatment under medical supervision by the Investigator or designee. The dose of study treatment and study subject identification will be confirmed at the time of dosing by a member of the study site staff other than the person responsible for study treatment accountability.

When subjects self-administer study treatment at home, the Investigator or designee will assess compliance with study treatment by counting the remained doses of FF/UMEC/VI in ELLIPTA as appropriate at the clinic visits and by querying the subject during the clinic visits as necessary, and document it in the source documents and CRF. A record of the number of the investigational product dispensed to and taken by each subject must be maintained and reconciled with study treatment and compliance records by the person responsible for study treatment accountability. Treatment start and stop dates will also be recorded in the CRF. Subjects should be  $\geq 80\%$  to  $\leq 120\%$  compliant on taking study treatment between each pair of scheduled and consecutive on-treatment clinic visits.

Subjects who fall outside this range should be re-educated on treatment compliance by their site. The Investigator should document this re-education in the source documents.

If the study treatment is withdrawn early or a subject is unable comply with the study treatment method and repeatedly falls outside the acceptable compliance range, the sponsor/monitor should be notified of it for discussion about appropriateness of continuation of the study in the subject.

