
 
• Immediately discontinue study treatment
 
• Report the event to GSK within 24 hours
 
• Complete the liver event CRF and complete an SAE data collection tool if the event also meets the criteria for an SAE
 
• Perform liver event follow up assessments (see Follow Up Assessments )
 
• Monitor the participant until liver chemistries resolve, stabilize, or return to within baseline (see MONITORING below)
 
• Do not restart/rechallenge participant with study treatment unless allowed per protocol and GSK Medical Governance approval is granted
 
• If restart/rechallenge not allowed or not granted, permanently discontinue study treatment and may continue participant in the study for any protocol specified follow up assessments
 
 
MONITORING:
 
For bilirubin or INR criteria:
 
 
• Repeat liver chemistries (include ALT, AST, alkaline phosphatase, bilirubin) and perform liver event follow up assessments within 24 hrs
 
• Monitor participants twice weekly until liver chemistries resolve, stabilize or return to within baseline
 
• A specialist or hepatology consultation is recommended
 
 
For All other criteria:
	
 
• Viral hepatitis serology
 
• Obtain INR and recheck with each liver chemistry assessment until the transaminases values show downward trend
 
• Only in those with underlying chronic hepatitis B at study entry (identified by positive hepatitis B surface antigen) and quantitative hepatitis B DNA
 
• Blood sample for pharmacokinetic (PK) analysis, obtained within 72 hours after last dose
 
• Serum creatine phosphokinase (CPK) and lactate dehydrogenase (LDH).
 
• Fractionate bilirubin, if total bilirubin <math>\geq</math> 2xULN
 
• Obtain complete blood count with differential count of leukocytes to assess eosinophilia
 
• Record the appearance or worsening of clinical symptoms of liver injury, or hypersensitivity, on the AE report form
 
• Record use of concomitant medications on the concomitant medications report form including acetaminophen, herbal remedies, other over the counter medications.
 
• Record alcohol use on the liver event alcohol intake case report form
 
 
For bilirubin or INR criteria:
 
 
• Anti-nuclear antibody, anti-smooth muscle antibody, Type 1 anti-liver kidney microsomal antibodies, and quantitative total immunoglobulin G (IgG or gamma globulins).
 

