6.1.5. Treatment Compliance

Treatment compliance will be assessed during the treatment period by dose group and total.

For the treatment period, the actual total number of doses received by each subject will be calculated as the sum of (dose counter start value – dose counter stop value) over all inhalers dispensed to the subject during the treatment period and returned prior to or at the EOT/EW visit, and percentage compliance will be calculated as follows:

$$\text{Treatment Compliance} = \frac{\text{total number of doses received}}{\text{treatment stop date} - \text{treatment start date} + 1} \times 100.$$

In interim analysis, treatment compliance will be calculated based on data until the day before visit 5 (i.e., treatment stop date will be replaced with the day before visit 5). Details on the derivations are provided in Section 11.6.2.

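### Investigational product collection is not scheduled at Early Withdrawal, yet the SAP counts only inhalers returned by that visit, so compliance of withdrawn participants can be understated

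*Protocol*

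**What the plan says.** **Schedule.** In Protocol Section 2, Table 1, the row "Collect investigational product" is marked at Visits 3, 4, 5, 6 and 7 and at the safety follow-up contact. The EW cell is empty. The copy in SAP 11.2.1 has the same pattern. The salbutamol collection row directly below is the reverse in these two columns: marked at EW, empty at follow-up.

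**Follow-up contact.** Protocol 5.1 says: "Telephone contact can be selected for follow-up period".

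**Return and counting in the protocol.** Section 7.1 says "All used and unused study treatment and salbutamol will be returned to GSK at the end of the study". Section 7.2 places the last dose in the clinic at Visit 7 or, as appropriate, at the early withdrawal visit. Section 7.6 assesses compliance "by counting the remained doses of FF/UMEC/VI in ELLIPTA as appropriate at the clinic visits", supplemented by questioning the participant, and requires reconciliation of product dispensed and taken. It also has treatment start and stop dates recorded in the CRF.

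**Compliance in the SAP.** Section 6.1.5 sums doses over inhalers dispensed in the treatment period and "returned prior to or at the EOT/EW visit", and divides by the number of days from treatment start to treatment stop. Section 11.6.2 repeats the restriction to returned devices, words the cut-off slightly differently (end of study or early withdrawal visit), and sets doses to missing for a container with no counter stop value.

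**The concern.** The SAP numerator presupposes that a withdrawn participant hands back the inhalers at EW. The schedule does not ask for that. It puts the next collection about a week later, after the SAP cut-off, at a contact where a device cannot be collected if it is made by telephone. Protocol Section 9 treats adherence to the schedule as required and allows no waivers. Sections 8.1.2 and 8.2 send sites to it for what to do at discontinuation and withdrawal, and Section 8.1.3 withdraws everyone who stops treatment. The EW column therefore governs every early stop at which the visit takes place.

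What is at stake is the compliance figure for these participants, and a clean count of doses used and outstanding in the group where dosing before an event is most likely to be queried.

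**Working it through.** **1. How many participants.** The plan enrols 110 so that about 100 complete, at about 10% drop-out (Protocol 10.1). Check: 110 × 0.90 = 99, and 100 / 0.90 = 111.1, so 110 agrees with the approximate rate. Early withdrawals: 110 × 0.10 = 11. At assumed rates of 5% and 15% the count is 5.5 and 16.5.

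**2. The rows side by side (Protocol Table 1).**

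| Row | Visit 2 | Visits 3–6 | Visit 7 | EW | Follow-up |
|---|---|---|---|---|---|
| Dispense product | X | X | – | – | – |
| Collect product | – | X | X | – | X |
| Collect salbutamol | X | X | X | X | – |

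**3. The SAP formula under literal adherence to the schedule.** Compliance = 100 × doses on inhalers returned by EW / (stop date − start date + 1). Assumptions:
- one dose every day without a miss;
- withdrawal between scheduled visits;
- nothing from the last dispensing returned at EW;
- the dose on a collection day comes from the new inhaler.

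With the last collection on Day v and stop on Day d, this is 100 × (v − 1) / d. Nominal visit days are 1, 29, 85, 169, 253 and 365.

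| Stop day d | Last dispensing day v | Counted / true doses | SAP compliance | SAP 11.6.2 band |
|---|---|---|---|---|
| 20 | 1 | 0/20 | 0% or missing | <50% if 0% |
| 60 | 29 | 28/60 | 46.7% | <50% |
| 84 | 29 | 28/84 | 33.3% | <50% |
| 127 | 85 | 84/127 | 66.1% | 50 to <80% |
| 168 | 85 | 84/168 | 50.0% | 50 to <80% |
| 200 | 169 | 168/200 | 84.0% | 80 to <95% |
| 252 | 169 | 168/252 | 66.7% | 50 to <80% |
| 309 | 253 | 252/309 | 81.6% | 80 to <95% |
| 364 | 253 | 252/364 | 69.2% | 50 to <80% |

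Day 20 is shown as 0% or missing because no inhaler has been returned by then, and the SAP does not say whether an empty sum is zero or missing. If the dose on a collection day came from the old inhaler, each later numerator rises by one, for example 29/60 = 48.3% and 169/200 = 84.5%. The error is small just after a visit (Day 254: 252/254 = 99.2%) and largest just before the next one.

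**4. With collection and counting at EW.** The numerator becomes d, so compliance is 100 × d / d = 100% at every stop day.

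**5. Stock outstanding.** Visit 6 to Visit 7 is 365 − 253 = 112 days, and 112 / 30 = 3.7. If the whole interval were supplied at once, that would be four inhalers or 120 doses. The documents do not give the number dispensed, so this is an assumption. On it, a withdrawal on Day 260 (8 doses used from that supply) would leave 120 − 8 = 112 doses to account for.

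**The case against.** The other side has real force on several points.

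- **Return is provided for.** Section 7.1 requires all study treatment to come back, Section 7.5 requires accountability and reconciliation, and the follow-up contact may be a clinic visit. A reader might infer that withdrawn participants keep their inhalers; the documents do not support that. However, Section 7.1 sets the return at the end of the study, which Section 5.3 defines as the last participant's final follow-up contact, so it does not fix a return at EW.
- **Counting is possible at EW.** Under Section 7.2 the inhaler in use may be in the clinic that day, and Section 7.6 allows a count. A reader might infer that the last doses can never be verified; that goes too far. But SAP 6.1.5 turns on the device being returned, so a counter read on a device that goes home again still falls outside its wording.
- **The schedule does not forbid return at EW.** An inhaler handed back there counts. The shortfall is a consequence of literal adherence, not a certainty for every withdrawal. The different cut-off wording in SAP 11.6.2 might also be read to admit later returns.
- **No conflict with the liver stopping rules.** "Immediately discontinue study treatment" in Appendix 6 concerns dosing. It says nothing about when a device is returned, and nothing in the schedule permits further dosing.
- **It may be a clerical slip.** The reversed salbutamol row suggests a mark set one column off. The documents do not confirm this. The SAP table reproduces the protocol's schedule, so it makes a text-reading error unlikely but is not separate evidence of intent.
- **Reach is narrow.** Stop dates come from the CRF, and the treatment period and treatment-emergent flag (SAP 11.4) are date-based.

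These points limit the consequence. They do not remove the mismatch between the schedule and the SAP return rule.

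**Conclusion.** The inconsistency stands. The schedule omits product collection at EW and places it after the SAP's return cut-off, while the SAP computes compliance as though collection happened at EW. Sections 7.2 and 7.6 of the protocol also sit more naturally with collection at that visit.

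Under the stated assumptions, a fully adherent participant who withdraws is reported at 0% or missing on Day 20, 47% on Day 60 and 84% on Day 200. Up to about 11 of 110 participants, 10% of the study, could be placed in the wrong compliance band. The actual number depends on how many sites collect inhalers at EW despite the blank cell, which the documents cannot tell us. Participants lost without an EW visit are outside this point.

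The effect is limited to Table 11.22 and Listing 57, their interim versions (Table 1.24 and Listing 14), and drug accountability. Adverse event incidence, the primary endpoint, does not depend on it.

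**What to change.** Treat this as device accountability and reconcile the row with the SAP return rule:

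1. In Protocol Table 1 and SAP 11.2.1, mark product collection at EW, and footnote the follow-up mark as applying only to inhalers not already returned.
2. State that the dose counter of every inhaler is read and recorded at EW.
3. Use one cut-off wording in SAP 6.1.5 and 11.6.2, and say whether a participant with no countable inhaler is shown as 0% or missing.

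The cost is one cell and a footnote in each schedule and a few words in the SAP. EW already includes an examination, ECG, laboratory samples and salbutamol collection, so no visit is added. Sample size and primary analysis are unchanged.
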